2.2 BACKGROUND

PTSD is a chronic impairment disorder that occurs after exposure to severe stressors (e.g., combat, natural disaster, or other traumatic events) (Miao et al. 2018). It is characterized by re-experiencing, avoidance, and hyperarousal symptoms, as well as negative alterations in cognition and arousal. These symptoms can lead to disturbances to the individual and their family, as well as significant medical, financial, and social problems.

Re-experiencing symptoms manifest as one of the following: recurrent, distressing recollections in the form of thoughts, perceptions, or dreams; feeling as if the traumatic event is happening again accompanied by illusions, hallucinations, and dissociative flashbacks; or intense psychological distress or physiological reactivity when exposed to internal or external cues reminiscent of the traumatic event(s) (American Psychiatric Association [APA] 2013; Jellestad et al. 2021). Avoidance symptoms are characterized by efforts to avoid thoughts, feelings, conversation, activities, places, or things that remind the individual of the traumatic event(s), as well as marked decrease in affect. Individuals with PTSD demonstrate negative alterations in mood and elevated levels of arousal, including problems initiating and maintaining sleep, increased irritability, hypervigilance, and hyperactive startle response, as well as difficulty concentrating. These symptoms can often lead to clinically significant distress and significant impairments in daily functioning.

A diagnosis, per Diagnostic and Statistical Manual of Mental Disorders, Version 5 (DSM-5) criteria, includes exposure to trauma and this trauma is persistently experienced through unwanted memory intrusions, nightmares, flashbacks, and emotional distress following an exposure to traumatic reminders (APA 2013). In addition, individuals avoid trauma-related stimuli and demonstrate negative alterations in cognition and mood, which may include overly negative thoughts about oneself and exaggerated blame of self or others for causing the trauma or negative affect.

According to the DSM-5, some individuals may receive a diagnosis of acute stress disorder in the first month following exposure to trauma (Bryant et al. 2016). In order to meet the criteria, an individual must present with at least nine symptoms from the categories of intrusion, negative mood, dissociation, avoidance, and arousal. These symptoms present at the beginning of the traumatic event or if these symptoms are pre-existing, then they worsen after the traumatic event. The duration of the disturbance is 3 days to 1 month following a trauma exposure. Although acute stress disorder and PTSD share similar requirements for diagnosis, there is a clear differentiation such that PTSD diagnosis requires meeting a certain number of symptoms within established clusters. This includes non-fear-based symptoms and a dissociative subtype, and the symptoms persist for longer than 1 month.

PTSD is generally associated with co-occurring psychiatric disorders and approximately 80% of patients with PTSD meet criteria for at least one other psychiatric condition (Brady 1997). The most common comorbidities are depression, alcohol and substance use disorders, anxiety disorders, physical health problems, and cognitive impairment (Kessler et al. 1995; Qureshi et al. 2011; Paccella et al. 2013). Common psychiatric comorbidities exacerbate PTSD symptoms and increase functional impairment (Ikin et al. 2010; Drapkin et al. 2011).

The National Comorbidity Survey Replication (NCS-R), which was conducted between 2001 and 2003, estimated the lifetime prevalence of PTSD among adult Americans to be 6.8% (NCS-R 2007a, 2007b). The lifetime prevalence of PTSD among men was 3.6% and among women was 9.7%. The reported prevalence of PTSD ranges from 5.4% to 16.8% among military service members and veterans, which is higher than among the general population (Miao et al. 2018). Genetic and epigenetic factors may account for up to 70% of the individual differences in PTSD development, with PTSD heritability estimated at 30%.

Most guidelines strongly recommend TF-psychological interventions as treatment options for PTSD, including CBT, cognitive-processing therapy (CPT), cognitive therapy (CT), cognitive restructuring (CR), coping skills therapy (including stress inoculation therapy), exposure-based therapies, eye movement desensitization and reprocessing (EMDR), hypnosis and hypnotherapy, and brief eclectic psychotherapy (APA 2017). Individual TF-CBT and EMDR have shown to be effective in reducing PTSD symptom severity (Bisson et al. 2013; Coventry et al. 2020). However, the quality of evidence showing superiority of TF-CBT and EMDR over waitlist and/or usual care comparison is low (Bisson et al. 2013). Furthermore, although psychological interventions have shown success in alleviating symptoms, there is no evidence for a significant improvement in affect dysregulation (Coventry et al. 2020). Additionally, psychological interventions, such as TF-CBT, EMDR, and mindfulness, do not show a maintenance of treatment effects at the 6-month follow up in veterans (Coventry et al. 2020). Various psychological interventions also show high dropout rates, with one review finding up to 54% (Schottenbauer et al. 2008) and another up to 65% (Lewis et al. 2020).

Furthermore, TF-therapies having a significantly higher dropout rate compared with non-TF therapies (Lewis et al. 2020). This could be reflective of patients' psychological preparedness to confront their trauma.

Pharmacological treatments for PTSD include antidepressants, such as SSRIs, SNRIs, and monoamine oxidase (MAO) inhibitors, sympatholytic drugs such as alpha-blockers, antipsychotics, anticonvulsants, and benzodiazepines (Coventry et al. 2020; Hoskins et al. 2015; Stein et al. 2006; Davidson et al. 2006a; Davidson et al. 2006b). The (U.S.) Food and Drug Administration (FDA) has approved two SSRIs for the treatment of PTSD: sertraline and paroxetine. These SSRIs primarily act upon the serotonin neurotransmitter system and have the strongest empirical evidence. Overall response rates with the use of SSRIs rarely exceed 60% in patients with PTSD and less than 20%–30% of patients achieve complete remission (Stein et al. 2002; Zohar et al. 2002). Other medications which are not approved for treatment of PTSD, such as fluoxetine, topiramate, risperidone, and venlafaxine, are also used in clinical practice. Maintenance of effect is also only observed through continued treatment, which suggests that the medication is addressing symptoms rather than the underlying source of the disorder (Asnis et al. 2004). Beyond SSRIs, a number of different research avenues have been explored, including prazosin and d-cycloserine but although some positive signals in small studies have been observed, these have typically not translated into larger confirmatory outcomes (de Kleine et al. 2012; Germain et al. 2012; Raskind et al. 2018). Patients with PTSD often receive treatment with multiple agents that often lack evidence of benefit, including diverse antidepressants, anxiolytics, mood stabilizers and antipsychotics (Davidson and Connor 1999; Keane et al. 2006; Miao et al. 2018).

Balovaptan is a brain penetrant, potent, and highly selective human V1a receptor antagonist that blocks the activation of the V1a G protein–coupled receptor.

In vitro, balovaptan exhibited an inhibition constant of 0.7 nM for the human V1a receptor with at least 1000-fold binding selectivity over 118 other receptors, enzymes, and ion channels, including human vasopressin 2 (V2) receptor, vasopressin 1b (V1b) receptor, and human oxytocin receptors.

Previous clinical studies of balovaptan have been conducted in healthy volunteers and participants with autism spectrum disorder (ASD) using the same dose (10 mg) as proposed for this study. In those trials, an estimated 448 subjects with ASD have received 10 mg once a day (QD) of balovaptan for at least 12 weeks, of whom approximately 326 subjects received 10 mg QD of balovaptan for at least 24 weeks. Balovaptan was found to be safe and well tolerated.

Detailed information on balovaptan is provided in the Balovaptan Investigator's Brochure.

2.3 BENEFIT–RISK ASSESSMENT

This study will assess the efficacy and safety of balovaptan in adults with moderate-to-severe PTSD. Currently, the first-line therapy for PTSD is individual TF-psychological interventions. However, these psychological interventions have not shown a significant improvement in affect dysregulation or maintenance of treatment effects at 6 month follow up in veterans (Coventry et al. 2020).

Areas in the brain that are rich in vasopressin receptors have been implicated in PTSD suggesting that arginine vasopressin (AVP) may be able to influence behavior that is relevant to PTSD (Torok et al. 2019). Nonclinical studies have shown that AVP agonists result in PTSD-like behavior in rodents (Sipos et al. 2020). In AVP-deficient Brattleboro rats, which have significant reduction of AVP signaling in the brain, demonstrated improved behavioral parameters that can be linked to PTSD symptoms. Furthermore, serum AVP concentrations have been observed to be higher in veterans with PTSD compared with those without (de Kloet et al. 2008). These findings imply that treatment with a V1a antagonist, such as balovaptan, may offer a means to alleviate symptoms of PTSD.

Across previous clinical trials of balovaptan, it has been found to be safe and well tolerated. This includes studies in healthy volunteers and in individuals with ASD (children, adolescents, and adults). No pattern of adverse events possibly characteristic for the use of balovaptan in humans has emerged to date.

The following are hypothetical or potential risks for balovaptan, based on its mechanism of action and available nonclinical data: seizure risk (animal studies), hematological toxicity (animal studies; mainly peripheral decrease in neutrophils), risk of bleeding (hypothetical relative to the mechanism of action), skeletal muscle toxicity (animal studies), cardiac toxicity (animal studies and interpreted to be stress related), blood pressure changes (hypothetical risk relative to the mechanism of action), and risk of peripheral neuropathy (animal studies) (for further details see [Appendix 6](#)). However, dedicated safety monitoring across clinical trials in healthy volunteers and in subjects with ASD have not revealed a safety signal with regard to the mechanism of action of balovaptan and animal-related potential safety risks.

The dose planned in this study is 10 mg QD, and this dose is the same as the highest dose administered in the ASD clinical trials which had a treatment duration of 12 weeks or longer. The safety monitoring planned in this study will continue to cover these hypothetical and animal-related safety considerations and is considered sufficient to ensure participant safety.

Refer to [Appendix 6](#) for information on potential risks for balovaptan and risk mitigation measures, including guidelines for managing adverse events.

More detailed information about the known and expected benefits and risks and reasonably expected events of balovaptan may be found in the Balovaptan Investigator's Brochure.

With the data thus far, the Sponsor believes the benefit–risk profile of balovaptan for participants in this study is favorable.

3. **OBJECTIVES, ENDPOINTS AND ESTIMANDS**

This study will evaluate the efficacy, safety, and pharmacokinetics of 10 mg QD balovaptan compared with placebo in participants with PTSD. Specific objectives and corresponding endpoints for the study are outlined in [Table 2](#).

Table 2 Objectives and Corresponding Endpoints

Primary Objective	
Efficacy Objective	Corresponding Endpoint

 To investigate the efficacy of balovaptan compared with placebo 	
 Change from baseline at Week 12 in the CAPS-5 total symptom severity score
Secondary Objectives	
Efficacy Objectives	Corresponding Endpoints

 To investigate the efficacy of balovaptan compared with placebo To investigate the efficacy of balovaptan compared with placebo in depression 	
 Change from baseline in symptom severity as measured by CGI-S after 12 weeks of treatment Change from baseline at Week 12 in the PHQ-9 total score
Safety Objective	Corresponding Endpoints

 To investigate the safety of balovaptan compared with placebo 	Safety will be assessed through the following: 
 Incidence and severity of adverse events, with severity determined according to a mild/moderate/severe grading scale Physical and neurologic examinations, vital signs, hematology, blood chemistry, including urinalysis ECGs and Doppler echocardiograms (the latter performed only in case of confirmed cardiac biomarker elevation) C-SSRS
Pharmacokinetic Objectives	Corresponding Endpoints

 To investigate the plasma pharmacokinetics of balovaptan 	
 Concentration per timepoint for balovaptan ^a PK parameters as appropriate

Table 2 Objectives and Corresponding Endpoints (cont.)

Exploratory Objectives	
Exploratory Biomarker Objective	Corresponding Endpoints

 To identify and/or investigate biomarkers that are predictive of response to balovaptan (i.e., predictive biomarkers) or are early signs of efficacy 	
 Relationship between biomarkers (e.g., EEG, genomics, digital biomarkers, computerized cognitive battery) and efficacy, safety, PK, or other biomarker endpoints (see Section 8.7)
Exploratory Efficacy Objectives	Corresponding Endpoints

 To investigate the efficacy of balovaptan compared with placebo 	
 Change from baseline at Week 12 on the CAPS-5 symptom cluster scores Proportion of participants with no symptoms, very mild, mild, moderate, severe, very severe in the PGI-S at each scheduled visit Proportion of participants with no change, improvement or worsening in the CGI-C and PGI-C at Weeks 6 and 12 Change from baseline at Week 6 on the CAPS-5 total symptom severity score

 To investigate the efficacy of balovaptan compared with placebo in PTSD symptoms, anxiety, sleep, functioning, and cognition 	
 Change from baseline at Weeks 6 and 12 on the following: 
 PCL-5 total score BAI total score PSQI total and domain scores CPFQ total score and domain scores SDS global score Computerized cognitive battery

BAI=Beck Anxiety Inventory; CAPS-5=Clinician-Administered PTSD Scale for DSM-5; CGI-C=Clinician-Global Impression of Change; CGI-S=Clinician-Global Impression of Severity; CPFQ=Cognitive and Physical Functioning Questionnaire; C-SSRS=Columbia-Suicide Severity Rating Scale; DSM-5=Diagnostic and Statistical Manual of Mental Disorders, Version 5; EEG=electroencephalogram; M2=Metabolite 2; M3=Metabolite 3; PCL-5=PTSD Checklist for DSM 5; PGI-C=Patient-Global Impression of Change; PGI-S=Patient-Global Impression of Severity; PHQ-9=Patient Health Questionnaire-9; PK=pharmacokinetic; PSQI=Pittsburgh Sleep Quality Index; PTSD=Post-traumatic stress disorder; SDS=Sheehan Disability Scale.

^a Concentration of M2 and M3 may be measured if indicated (e.g., safety concern).

The clinical question of interest is to assess the study treatment effect of 10 mg QD balovaptan compared with placebo in terms of the change from baseline at Week 12 in the Clinician-Administered PTSD Scale for DSM-5 (CAPS-5) irrespective of adherence to randomized treatment.

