1.3 SCHEDULE OF ACTIVITIES

Table 1 Schedule of Activities

	Screening	Pre-Rand. Visit	Blinded Treatment Period						Safety Follow-Up ^a	Early Discont. ^{b, c}
Week			0	2	4 ^d	6	9 ^d	12	14	
Study Day(s)	-28 to -1	-7 to -1	1	14	28	42	63	84	98	
Visit window (days)				±3	±3	±3	±3	±3	-3/+7	
Informed consent ^e	x									
Medical history, demographics, and baseline conditions ^f	x									
Resting-state EEG ^g		x ^h		x		x		x		x ⁱ
Urinalysis ^j	x								x	x
Urinalysis for substance abuse ^k	x		x			x		x	x	x
Serology (HIV, and hepatitis B and C) ^l	x									
Coagulation ^m	x							x		x
Pregnancy test ⁿ	x		x			x		x		x
Weight and height (height to be measured at screening only)	x							x		x
Vital signs ^o	x		x	x		x		x	x	x
PK blood sample ^p				x		x		x		x
Clinical genotyping sample ^q			x							
Blood sample for WGS ^r			x							
RBR blood sample (optional) ^s				x						

Table 1 Schedule of Activities (cont.)

	Screening	Pre-Rand. Visit	Blinded Treatment Period						Safety Follow-Up ^a	Early Discont. ^{b, c}
Week			0	2	4 ^d	6	9 ^d	12	14	
Study Day(s)	-28 to -1	-7 to -1	1	14	28	42	63	84	98	
Visit window (days)				±3	±3	±3	±3	±3	-3/+7	
Complete physical examination ^t	x		x					x	x	x
Limited physical examination ^t						x				
Neurologic evaluation (upper and lower limbs)	x		x			x		x	x	x
Clinical signs and symptoms of infection ^u					x	x	x	x		
12-Lead ECG ^v	x		x	x				x	x	x
Hematology ^w	x		x			x		x	x	x
Full serum chemistry ^x	x		x			x		x	x	x
Quantitative immunoglobulins (IgA, IgG, IgM, and IgE)			x					x		x
PCL-5	x		x	x		x		x		x
SCID-5	x									
LEC-5	x									
CAPS-5 (administered by central rater)		x ^h				x		x		x
CGI-S			x			x		x		x
CGI-C						x		x		x
PGI-S			x			x		x		x
PGI-C						x		x		x

Table 1 Schedule of Activities (cont.)

	Screening	Pre-Rand. Visit	Blinded Treatment Period						Safety Follow-Up ^a	Early Discont. ^{b, c}
Week			0	2	4 ^d	6	9 ^d	12	14	
Study Day(s)	-28 to -1	-7 to -1	1	14	28	42	63	84	98	
Visit window (days)				±3	±3	±3	±3	±3	-3/+7	
Beck Anxiety Inventory			x			x		x		
Pittsburgh Sleep Quality Index			x			x		x		
PHQ-9			x			x		x		x
C-SSRS ^y	x	x	x	x	x	x	x	x	x	x
SDS			x			x		x		
CPFQ			x			x		x		
Computerized cognitive battery		x ^h		x		x		x		x
Wearable heart rate, step count, and sleep monitoring device (e.g., OURA™ Ring)		x ^z	x	x	x	x	x	x		x
Previous and concomitant medications ^{aa}	x		x	x	x	x	x	x	x	x
Adverse events ^{bb}	x	x	x	x	x	x	x	x	x	x
Study drug dispensation ^{cc}			x			x				
Study drug accountability				x	x	x	x	x		x

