Table 1 Schedule of Activities (cont.)

CAPS-5=Clinician-Administered PTSD Scale for Diagnostic and Statistical Manual of Mental Disorders, Version 5; CGI-C=Clinician Global Impression of Change; CGI-S=Clinician-Global Impression of Severity; CPK=creatine phosphokinase; CK-MB=creatine kinase-MB; CPFQ=Cognitive and Physical Functioning Questionnaire; C-SSRS=Columbia-Suicide Severity Rating Scale; cTnl=cardiac troponin; DSM-5=Diagnostic and Statistical Manual of Mental Disorders, Version 5; eCRF=electronic Case Report Form; EEG=electroencephalogram; HBcAb=hepatitis B core antibody; HBsAg=hepatitis B surface antigen; HCV=hepatitis C virus; HDL=high-density lipoprotein; hs-cTnT=high-sensitivity-cardiac troponin T; LDH=lactate dehydrogenase; LDL=low-density lipoprotein; LEC-5=Life Events Checklist for DSM-5; PCL-5=PTSD Checklist for DSM-5; PCP=phencyclidine; PGI-C=Patient Global Impression of Change; PGI-S=Patient Global Impression of Severity; PHQ-9=Patient Health Questionnaire-9; PK=pharmacokinetic; PTSD=post-traumatic stress disorder; QTc=corrected QT interval; Pre-Rand=randomization; SCID-5=Structured-Clinical Interview for DSM-5; SDS=Sheehan Disability Scale; RBR=Research Biosample Repository; UV=unscheduled visit; ULN=upper limit of normal; WGS=whole genome sequencing.

Notes: On treatment days, all assessments should be performed prior to dosing, unless otherwise specified.

The visit window is ± 3 days, and all assessments should be completed within the visit window. *Following any visit that may occur outside of allowable visit window*, participants should return to the initial planned schedule (per randomization *as Day 1*) for all subsequent visits. For participants who terminate early, assessments listed under the early discontinuation visit should be completed. For safety follow up, the visit window is $-3/+7$ days and all safety assessments should be completed within the visit window.

Unscheduled visits may be performed if clinically indicated. The following assessments should be performed at a minimum: concomitant medications, adverse events, and vital signs. Additional safety assessments may be performed as clinically indicated, per investigator discretion.

- ^a A safety follow-up visit must occur for all participants at 2 weeks following their last study treatment dose.
- ^b To be conducted if a participant discontinues from the study or study-drug treatment prematurely.

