- ^c All participants who withdraw or discontinue from the study treatment early will be asked to return as soon as possible (and within 2 weeks after the last dose of study drug) for an early discontinuation visit, unless the withdrawal occurs within 2 weeks of the Week 12 visit.
- ^d Participants will be called by the site personnel to monitor safety and tolerability when not attending the clinic. *In the event that the participant cannot be reached, at least 3 documented attempts to contact the participant for these visits must occur.*
- ^e Informed consent must be documented before any study-specific screening procedure is performed, and may be obtained more than 28 days before initiation of study treatment.
- ^f Medical history includes clinically significant diseases, surgeries, reproductive status, smoking history, use of alcohol and drugs of abuse, and all medications (e.g., prescription drugs, over-the-counter drugs, vaccines, herbal or homeopathic remedies, nutritional supplements) used by the participant within 24 weeks prior to the screening visit as well as details of psychosocial or non-pharmacological interventions used during the previous 24 weeks. Demographic data will include age, sex, and self-reported race/ethnicity. Participants will also be asked about their residential setting, school, or employment status, level of education, participation in educational or day programs, and any non-medical hospitalizations.
- ^g EEG: Two runs each of resting eyes open and eyes closed.

Table 1 Schedule of Activities (cont.)

- ^h These assessments should be completed no more than 7 days prior to the baseline visit and will be considered the baseline measure.
- ⁱ EEG to be conducted if a participant discontinues study treatment before Week 6.
- ^j Urinalysis will be performed at the site by dipstick for blood, protein, glucose, ketones, specific gravity, and pH. Microscopic examination performed at the central laboratory if blood and/or protein results are positive or strongly positive. If there is an explanation for the positive dipstick results (e.g., menses), it should be recorded and there is no need to perform microscopy and culture.

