- ^k Urine samples will be analyzed for the presence of drugs such as: alcohol, cannabinoids, opiates, cocaine, barbiturates, methadone, and PCP. Results will be used to verify participant eligibility pertaining to drugs of abuse. Inconclusive results may be repeated once during the screening period. Investigators should use their best clinical judgment in cases where results may be erroneous (e.g., permitted use of opiates or ingestion of food or food supplements).
- ^l Viral serology includes HIV (specific tests for HIV-1 antibody, HIV-1 and -2 antibodies, and HIV-2 antibody), HBsAg, HBcAb, and HCV antibody.
- ^m Coagulation assessments include INR, aPTT, and PT.
- ⁿ Females of childbearing potential (including those who have had a tubal ligation) will have a serum pregnancy test at screening and must have a urine pregnancy test performed at the site prior to each dose administration at the specified visits. If a urine pregnancy test is positive, it must be confirmed by a serum pregnancy test at the central laboratory. Results are to be recorded only in the source documents.
- ^o Vital signs include measurements of respiratory rate, pulse rate, and systolic and diastolic blood pressure while the participant is in a seated position, and body temperature. Vital sign assessments should be performed just prior to study drug administration. All vital signs should be recorded on the eCRF. *Three consecutive blood pressure readings will be recorded at intervals of at least 1 minute. The average of the three blood pressure readings will be recorded on the eCRF.*
- ^p PK samples should be obtained just prior to study drug administration, if possible. At Week 6, two PK samples will be taken (pre- and post-dose). Following the pre-dose sample, at the start of the study visit, the participant will receive study drug. A post-dose sample can be taken at any time between 3 hours after study drug administration and the end of the study visit. Accurate recording of the time of study drug administration and sample collection is critical.
- ^q Can be collected on any study visit if not collected at baseline visit.
- ^r Not applicable for a site that has not been granted approval for WGS.
- ^s Not applicable for a site that has not been granted approval for RBR sampling. Perform only for participants at participating sites who have provided written informed consent to participate.

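### Urinalysis is a named safety assessment, but Table 1 schedules none during dosing, so there is no systematic on-treatment comparison between arms

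*Combined protocol and SAP*

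**What the plan says.** The synopsis (Section 1.1) and Table 2 (Section 3) give the safety objective as a comparison with placebo and list among its endpoints "Physical and neurologic examinations, vital signs, hematology, blood chemistry, including urinalysis". Appendix 2, Table A2-1, includes urinalysis among the required safety laboratory tests.

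The timing is set in Table 1 (Section 1.3). Footnote j defines the test: "Urinalysis will be performed at the site by dipstick for blood, protein, glucose, ketones, specific gravity, and pH". Central microscopy follows when blood or protein is positive, unless there is an explanation for the result. The row is marked at three of the ten visit columns: screening, the Week 14 safety follow-up and early discontinuation.

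A separate row, "Urinalysis for substance abuse ^k", is marked at screening, Weeks 0, 6, 12 and 14, and early discontinuation. Footnote k gives its content: "Urine samples will be analyzed for the presence of drugs such as: alcohol, cannabinoids, opiates, cocaine, barbiturates, methadone, and PCP".

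On the follow-up visit, footnote a says: "A safety follow-up visit must occur for all participants at 2 weeks following their last study treatment dose". The early discontinuation column is limited by footnote b: "To be conducted if a participant discontinues from the study or study-drug treatment prematurely". Footnote c and Section 7.1 allow that visit to take place up to 2 weeks after the last dose.

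**The concern.** A safety assessment meant to inform a drug-versus-placebo comparison should be measured at least once while participants are taking the drug. Urinalysis is not. In completers, the only value that can be set against screening is taken after dosing has ended. A urinary finding (blood, protein, glucose, ketones, specific gravity or pH) that arises on drug and clears within two weeks of stopping would leave no trace in the scheduled data. Clean Week 14 results could then be read as evidence about urinary safety on balovaptan, which they are not.

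**Working it through.** The plan states no figure to reproduce, so the check is a reading of the schedule and simple day counts.

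**Step 1. Is the gap real or a broken table?** Each Table 1 row was mapped to the ten visit columns: screening, pre-randomization, Weeks 0, 2, 4, 6, 9 and 12, Week 14 follow-up, and early discontinuation. The urinalysis row has all ten cells, and the other laboratory rows map sensibly in the same way.

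| Test | Marked at | Scheduled between first dose and end of dosing (completer) |
|---|---|---|
| Dipstick urinalysis | Screening, Week 14, early discontinuation | 0 |
| Urine drug screen | Screening, Weeks 0, 6, 12, 14, early discontinuation | 2 (Weeks 6, 12) |
| Hematology | Screening, Weeks 0, 6, 12, 14, early discontinuation | 2 (Weeks 6, 12) |
| Serum chemistry | Screening, Weeks 0, 6, 12, 14, early discontinuation | 2 (Weeks 6, 12) |
| Coagulation | Screening, Week 12, early discontinuation | 1 (Week 12) |
| Immunoglobulins | Weeks 0, 12, early discontinuation | 1 (Week 12) |

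Week 0 samples precede the first dose and are not counted. Among these tests, urinalysis alone has no on-treatment visit.

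**Step 2. Does another section add a timepoint?** Section 8.2.5 refers timing back to Table 1. Appendix 2 lists the test without adding a visit. The urine drug screen looks for drugs of abuse and does not report the dipstick analytes.

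**Step 3. How far off drug is a completer's one post-baseline result?** Inputs are the study days and windows in Table 1, taking the last dose as given at the Week 12 visit.

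- Nominal: Day 98 - Day 84 = 14 days.
- With the follow-up window of -3/+7 days: 95 - 84 = 11 to 105 - 84 = 21 days.
- If the Week 12 visit also moves by up to 3 days either way and the follow-up keeps to the planned calendar: 95 - 87 = 8 to 105 - 81 = 24 days.

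The documents give no half-life, so residual exposure at that point cannot be judged from them.

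**Step 4. Do early discontinuers supply on-drug results?** Not reliably. Their visit may fall anywhere up to 2 weeks after the last dose, so a result may be as far off drug as a completer's nominal 14 days.

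**Step 5. What is the baseline?** Section 9.4.1 takes the last assessment up to and including the day of first dose. With no Week 0 mark, that is the screening urinalysis. A completer's change from baseline is thus a pre-treatment value against a post-treatment one.

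**The case against.** The strongest reply is that this is a coverage choice and not a contradiction. Table 2 gives no timepoint and does not promise an on-treatment urinalysis. Section 2.3 lists seizure, hematological, bleeding, skeletal muscle, cardiac, blood pressure and peripheral nerve risks, none of them primarily urinary. Creatinine, BUN or urea, electrolytes, albumin and glucose are measured at Weeks 6 and 12. Adverse events are collected throughout, and the investigator may order further tests. With about 30 participants and descriptive analysis only, a few more dipsticks would settle little. All of this stands, and it is why the point is minor. It does not supply a systematic on-treatment urinalysis in both arms, and no reason is given for scheduling this test differently from the other laboratory tests.

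Three stronger readings are tempting and are not supported.

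- A reader might infer that the analysis would set off-drug values in completers against near-treatment values in dropouts. Footnote a makes every participant due the follow-up visit 2 weeks after the last dose, Section 9.4.5 displays relevant laboratory data by time, and the objective contrasts balovaptan with placebo. Nothing says that the two kinds of visit are pooled.
- A reader might try to count how many of the 30 would have a result near treatment. The current text gives no dropout rate, and a discontinuation visit is not assured to be near treatment.
- A reader might infer that on-drug renal or urinary effects cannot be seen at all. Chemistry, adverse events and unscheduled tests could reveal some, and a change that lasts two weeks off drug could appear at Week 14.

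**Conclusion.** The point holds as a minor gap in coverage. A completer has 0 scheduled urinalyses during 12 weeks of dosing, against 2 each for hematology and chemistry. The only post-baseline value falls nominally 14 days after the last dose. No participant is guaranteed an on-drug result, so the trial cannot describe on-treatment urinary findings systematically by arm. This rests on the marks in Table 1 being as intended and on the last dose being taken at about Week 12. It does not rest on any assumed dropout rate or on a known urinary effect of balovaptan.

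**What to change.** In Table 1, add the dipstick urinalysis at Week 12, and preferably also at Week 6. Urine is already collected from all participants at both visits for the drug screen, so no new visit or sample is needed. Keep the Week 14 test, because it is the only scheduled post-treatment check in completers.

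The cost is a table edit, at most 30 x 2 = 60 dipsticks (30 if only Week 12 is added), and central microscopy when blood or protein is positive.

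If the schedule is left unchanged, state in Table 2 and Section 9.4.5 that urinalysis is assessed only before and after treatment and does not describe urinary safety on treatment. That costs two sentences.
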